We estimate a total sample size of 1080 children with SAM (360 per arm) and 1080 children with MAM (360 per arm) will provide at least 90% statistical power to demonstrate non-inferiority for each comparison, with a non-inferiority margin of 10 percentage points, assuming a recovery rate in the control of 77% (Table 4). For relapse outcomes, sample size will be smaller, and thus power will be lower, because only recovered children will be included in the analysis. All calculations assume a one-sided $\alpha = 0.05$ for non-inferiority and two-sided $\alpha = 0.05$ for superiority analyses.

Table 4. Sample size calculations

Scenarios with at least 80% power are **bolded**.

Primary outcome	Analysis type	Sample size per arm	Outcome prevalences reported in literature	Non-inferiority margin or detectable effect size	Assumption on control group outcome prevalence/means in sample size calculations	Power per comparison
Anthropometric recovery at discharge	Non-inferiority	360 MAM and 360 SAM children/arm enrolled; 306 MAM and 306 SAM children in analysis after 15% attrition	MAM recovery (with RUSF*): 73% (13); 73% (14); 85% (15) SAM recovery : 55.4% (16); 82.3% (17); 76% (18); 71% (pooled estimate from meta-analysis) (19)	10 percentage points (absolute difference)	55.4% (vs 45.4%)	85.6%
					77.0% (vs 67.0%)	90.0%
					82.3% (vs 72.3%)	96.8%
Relapse to wasting within 3-months post-discharge	Superiority	236 children/arm in analysis (assuming 77% of the 306 children recover)	Post-MAM relapse : 30% within 3 months (period prevalence) (20); 33% within 12-months (21) Post-SAM relapse : 6.8% 3-month cumulative incidence (22); 24% 2-month cumulative incidence (23); 30% within 3-months (unpublished); 2.6 episodes per child-year (unpublished); 1.3	35% relative reduction (incidence rate ratio = 0.65)	Incidence of 2.6 episodes per child-year	80.0%
					Prevalence of 30% (vs 20%)	71.0%

			episodes per child-year (unpublished)			
--	--	--	--	--	--	--

*RUSF = ready-to-use supplementary food

Study procedures

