### Sample size and statistical power

#### Main trial

We estimate a total sample size of 1080 children with SAM (360 per arm) and 1080 children with MAM (360 per arm) will provide sufficient statistical power to demonstrate non-inferiority for each comparison, with a non-inferiority margin of relative 12.5%, assuming a recovery rate in the control of 76% and a loss to follow up of 15% (Table 4). The sample size will be smaller for analyses of relapse, because only recovered children will be included in the analysis. All calculations assume a one-sided  $\alpha = 0.05$  for non-inferiority and two-sided  $\alpha = 0.05$  for superiority analyses,  $\beta = 0.8$ , and 15% attrition. While the key objectives of this research are to evaluate effects of the alternative RUTFs on recovery and relapse, we consider as primary outcomes any outcome for which we have adequate power for clinically or policy meaningful effect sizes (5).

 Stata commands `ssi` for continuous outcomes and `artbin` for binary outcomes were used for non-inferiority analyses, and `power twomeans` for continuous outcomes and `power twoproportions` for binary outcomes were used for superiority analyses. Outcome proportions, means, or standard deviations were taken from relevant studies in literature as delineated in Table 4.

Table 4. Calculations of detectable effect sizes for all outcomes

Outcome	Outcome prevalence in the literature	Type of analysis	Non-inferiority margin (relative) with $\geq 80\%$ power (Non-inferiority)	Detectable effect size at 80% power (Superiority)	Rank of outcome
Anthropometric recovery at discharge	MAM recovery (with RUSF*): 73% (6); 73% (7); 85% (8)  SAM recovery: 55.4% (9); 82.3% (10); 76% (11); 71% (pooled estimate from meta-analysis) (12)	Non-inferiority	12.5% relative margin		Primary
Relapse to wasting within 3-months post-discharge	Post-MAM relapse: 30% within 3 months (13); 33% within 12-months (14)  Post-SAM relapse: 6.8% 3-month cumulative incidence (15); 24% 2-month cumulative incidence (16); 30% within 3-months (unpublished)	Superiority		Risk difference of 11%; Relative risk = 0.72	Primary
Length of stay (LOS) among recovered children	MAM: 36.4 days (SD 50.4 days)(17); 5.9 weeks (95% CI: 4.9, 7.0)(18) SAM: 56 days (assumed 41 day SD) (9)	Non-inferiority	MAM: 4.9 days; 12.5% relative margin SAM: 8 days; 12.5% relative margin		Primary

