## Statistical methods

We will conduct two separate comparisons between (i) the control group and SMS-RUTF, and (ii) between the control group and S-RUTF. All analyses will be done separately by wasting severity status (MAM vs SAM); that is, all analyses will be conducted and presented among MAM children and among SAM children separately. No adjustments for multiple comparisons will be made.

For binary outcomes, we will use log-binomial regression to estimate relative risks (RRs) and 95% confidence intervals (CIs) for the RRs, adjusting for any baseline factors as appropriate (described further below). If the regression model is adjusted, we will present both crude (unadjusted) and adjusted model results. If the models do not converge, we will use Poisson regression models with robust estimation of standard errors (26) and report which model was used. Non-inferiority will be declared if the lower bound of a one-sided 95% CI for the RR lies entirely below the non-inferiority margin of a relative 12.5%. For superiority analyses, we will use a two-sided 95% CI and superiority will be declared if the lower bound of the 95% CI for the relative risk is above 1.0. All analyses will be adjusted for health center to reflect the stratified randomization (27–29).

For continuous outcomes measured at one timepoint, we will use linear regression to estimate differences in that outcome between treatment arms, adjusting for any baseline factors as appropriate and health center (as explained above). Both unadjusted and adjusted model results will be presented.

For any outcome for which non-inferiority is demonstrated, we will then sequentially test for superiority. In these cases, we will report both non-inferiority and superiority results. The superiority analysis will be considered exploratory, as the study power calculations were based on non-inferiority effect size.

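### The detectable effect printed in SAP Table 4 for relapse to wasting (11 points with RR 0.72) fits no listed control relapse rate; at 30% control relapse the relative risk that goes with 11 points is about 0.63

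*SAP*

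**What the plan says.** In SAP Table 4 the row for relapse to wasting within 3 months is a superiority row with the rank primary. Its entry in the column for the effect detectable at 80% power is "Risk difference of 11%; Relative risk = 0.72". One entry serves both MAM and SAM, and no control rate is attached to it. The literature column lists 30% within 3 months and 33% within 12 months after MAM. After SAM it lists 6.8% at 3 months, 24% at 2 months and 30% at 3 months.

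The text above the table sets the inputs: 360 children per arm in each stratum, "assuming a recovery rate in the control of 76% and a loss to follow up of 15" percent, and a smaller sample for relapse "because only recovered children will be included in the analysis". A footnote names a two-proportion power command for binary superiority outcomes. In SAP Statistical methods, superiority on a binary outcome is judged on a relative risk, for which "we will use a two-sided 95% CI".

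Protocol Table 4 treats 30% as the control relapse rate: 30% against 20%, 236 per arm, 71.0% power.

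Two sibling rows in SAP Table 4 give RR 0.689 for relapse to MAM and RR 0.34 for relapse to SAM. Both note that 88.6% of relapses are assumed to be MAM.

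**The concern.** A risk difference and a relative risk together fix the control rate, so a pair that matches no listed control rate has something wrong in it. This pair is the SAP's only statement of what the trial can show on relapse, one of its two key objectives. The SAP also says that it ranks outcomes as primary where power is adequate for a meaningful effect, so the cell supports that ranking. A reader would take from it that a 28% relative reduction can be detected with 80% power. If control relapse is near 30%, the reduction detectable with that power is nearer 37%.

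**Working it through.** **Inputs.** Enrolled per arm and stratum 360, loss 15%, recovery 76% (SAP, Sample size and statistical power). Analysed n = 360 x 0.85 x 0.76 = 232.6, about 233. Alpha is 0.05 two-sided, with 1:1 allocation per comparison. The 30% control rate is the Protocol's.

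**Formula** (pooled two-proportion test, p̄ the mean of the two rates):

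power = Φ{ [ |p1 − p2|√n − 1.96√(2p̄(1 − p̄)) ] / √(p1(1 − p1) + p2(1 − p2)) }

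**Step 1: reproduce the Protocol.** For 30% against 20% with n = 236: (0.10 x 15.362 − 1.96 x 0.6124)/0.6083 = 0.552, so power is 71.0%, as printed. The method matches the trial's own.

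**Step 2: control rate implied by the SAP pair.** 0.11/(1 − 0.72) = 39.3%. Rounding of both figures allows 0.105/0.285 = 36.8% to 0.115/0.275 = 41.8%. No listed rate lies in that range. Even at 39.3% against 28.3%, n = 233 gives 71% power, and 80% would need about 290 per arm.

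**Step 3: power for RR 0.72 with n = 233.**

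| Control rate | Intervention rate | Difference (points) | Power |
|---|---|---|---|
| 33% (12-month figure) | 23.8% | 9.2 | 60% |
| 30% | 21.6% | 8.4 | 54% |
| 24% | 17.3% | 6.7 | 43% |
| 6.8% | 4.9% | 1.9 | 14% |

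For the 30% line: (0.084 x 15.264 − 1.96 x 0.6188)/0.6159 = 0.113, so power is 54.5%. Unpooled variance, a log-RR test and simulation give 53.5% to 54.9%. One-sided alpha gives 66.6%. Using n = 274, 306 or 360 gives 61.4%, 66.2% and 73.2%. None reaches 80%. RR 0.72 at 30% needs 425 analysed per arm.

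**Step 4: which half of the pair reproduces.** At 30% and n = 233, 30% against 19% (11 points) has 79.0% power. Solving for exactly 80% gives 30% against 18.9%: 11.1 points, RR 0.189/0.300 = 0.63. The risk difference stands at 30%, and the relative risk does not.

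**Step 5: a possible source.** Take 30% as the lower (intervention) rate and solve upward. With n = 360 x 0.76 = 274, omitting the 15% loss, the result is 41.4% against 30%: 11.4 points, RR 0.724. Both round to the printed figures, and this holds for n from 272 to 277. With n = 233 the upward solution is 12.4 points, RR 0.71, which does not match.

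**Step 6: sibling rows**, assuming that 30% is the base rate. Relapse to MAM is 30% x 0.886 = 26.6%; relapse to SAM is 30% x 0.114 = 3.4%.

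| Row | Printed RR | Solved upward, n = 233 to 236 | Solved downward, n = 233 to 236 |
|---|---|---|---|
| Relapse to MAM | 0.689 | about 0.69 | about 0.60 |
| Relapse to SAM | 0.34 | about 0.35 | 0.01 to 0.02 |

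Both fit upward solving and neither fits downward solving.

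**The case against.** The SAP row names no control rate, so the power of RR 0.72 depends on the one that is assumed. At the Protocol's other scenario, 2.6 episodes per child-year with rate ratio 0.65, three-month risks are 1 − exp(−0.65) = 47.8% and 1 − exp(−0.4225) = 34.5%. That is RR 0.72 with about 83% power at 233 per arm. This is fair as far as it goes, but the difference is then 13.3 points, not 11, and the SAP row no longer lists that rate.

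The pair can also be generated from a listed rate, by the upward solution in step 5. A reader might infer that the two figures are incompatible with every listed rate on any reading, and that is too strong: they are incompatible with every listed rate read as the control rate. The upward reading does not rescue the entry. It assumes control relapse of about 41%, which is not listed, and drops the attrition that the SAP says it applied.

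A reader might further infer a flat contradiction with the Protocol, which gives 71.0% power to a larger relative effect (RR 0.67). That follows only if the SAP also assumes 30% control relapse, and it does not say so. What can be said is that the two tables cannot be reconciled as printed.

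Finally, the sample size is justified on non-inferiority of recovery, and the Protocol says openly that power for relapse is lower. That stands, and it limits the point to the stated figures.

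**Conclusion.** The relapse-to-wasting entry is wrong as printed. With 30% control relapse, about 233 recovered children per arm per stratum and two-sided alpha 0.05, the effect detectable with 80% power is about 11 points, RR 0.63. RR 0.72 then has about 54% power. The 30% is the Protocol's control rate, not one that the SAP row states; if control relapse is 24%, the power for RR 0.72 is 43% and the detectable RR is 0.58.

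The problem probably reaches all three relapse rows, since all three fit solving upward from a listed rate. That origin is an inference from the numbers, as the documents do not show the calculation.

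Two stronger conclusions are not supported. The first is that the trial is close to a coin toss for a 28% reduction whatever the relapse rate; that holds only near 30%. The second is that a null result would be taken to exclude such a reduction: the analysis reports a confidence interval, and the interval will show what is excluded.

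**What to change.** For each of the three relapse rows in SAP Table 4, state the assumed control rate and the analysed number per arm, separately for MAM and SAM, and recompute the detectable effect downward from the control rate. At 30% and 233 per arm, restate the relapse-to-wasting entry as about 11 points (RR 0.63). Delete RR 0.72, or keep it with its power at the stated control rate. Because the SAM rates listed run from 6.8% to 30%, show the SAM entry at more than one rate. Align the result with Protocol Table 4 (30% against 20%, 71.0% power).

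The cost is a table revision and a short recalculation. Enrolment, test and analysis model are untouched. The stated detectable effects become less favourable.

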## Study interventions

Children admitted into MAM or SAM treatment at the study centers will be randomized to one of three RUTF formulations:

- **Standard of care RUTF (control):** composed of milk powder, sugar, vegetable oil, peanut butter, vitamins, and minerals and low in fiber (~0.75g per 100g)
- **SMS-RUTF (intervention 1):** a milk- and peanut-free product with added crystalline amino acids that provide significantly more fiber (~5.0g per 100g)
- **S-RUTF (intervention 2):** a reduced-milk product

Burkina Faso national guidelines for MAM and SAM ambulatory treatment will be followed for dosing the products and all other aspects of treatment (4). Thus, all children will receive the standard of care for Community Management of Acute Malnutrition (CMAM) treatment in Burkina Faso, with the only difference between treatment arms being the product received. Burkina Faso national guidelines for CMAM are detailed in the guideline document (4). Briefly, upon admission to treatment for SAM, children will undergo medical evaluation and appetite test and receive routine antibiotics and rapid diagnostic test for malaria as well as other treatments as indicated in the guidelines. Caregivers of eligible children will be provided with RUTF and instructed on how to use it. Children will be followed weekly at the health center to be re-evaluated. At the follow-up visits, children's anthropometry will be measured, a clinical examination will be performed, and the caregiver will be provided with another 7-days' supply of RUTF with instructions. Children will be treated for a maximum of 12 weeks and will be eligible to be discharged when they have achieved anthropometric recovery (see definition below). For MAM, upon admission to treatment, children will be provided with RUTF to be used as a food supplement in addition to the child's usual diet. Caregivers will be provided with the product and instructed on its use and receive nutritional counseling as per guidelines. Children will receive medical treatments as indicated in the guidelines and instructed to return to the health facility every two weeks for monitoring. Children will be treated for a maximum of 12 weeks and be eligible for discharge when they have achieved anthropometric recovery.

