## Study outcomes

### Main trial

The primary and secondary outcomes for the main trial and their definitions are listed in Table 1. Outcomes are the same for MAM and SAM children.

*Table 1. Primary and secondary efficacy outcomes*

Outcomes	Definition	Type of analysis
Primary outcomes		
Anthropometric recovery at discharge	WLZ $\geq$ -2 and MUAC $\geq$ 125 mm and absence of bilateral pitting edema for two consecutive visits, at the day of end of treatment	Non-inferiority
Relapse to wasting within 3 months post-discharge	A new episode of wasting (defined as WLZ/WHZ $<$ -2 or MUAC $<$ 125 mm or presence of bilateral pitting edema) within the 3-month period following recovery from the index wasting episode, among children who recovered from their index episode	Superiority
Length of stay (LOS) among recovered children	The number of days between the day the child is admitted to treatment and the day the child is determined to be recovered and thus discharged from treatment	Non-inferiority
Weight gain	Change in child's weight (gram/kilogram/day) between weight on day of admission to treatment and the day of end of treatment	Non-inferiority
Anthropometry at discharge from treatment	WLZ/WHZ, MUAC, weight, height/length, LAZ/HAZ and WAZ at the day of end of treatment	Non-inferiority
Anthropometry at 3-months post-discharge	WLZ/WHZ, MUAC, weight, height/length, LAZ/HAZ and WAZ at 3-months post-discharge (3 months after the day of end of treatment)	Superiority
Hemoglobin at discharge	Hemoglobin concentration (grams/liter) at the day of end of treatment	Non-inferiority
Hemoglobin at 3-months post-discharge	Hemoglobin concentration (grams/liter) at 3-months post-discharge (3 months after the day of end of treatment)	Superiority
Secondary outcomes		
Default from treatment	Child is absent for two consecutive visits, declared a defaulter on the second visit	Non-inferiority

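### SAP Table 4, length of stay: the MAM SD of 50.4 days cannot occur under the 12-week cap, and the printed SDs, recovered-only sample, margins and 80% power do not agree

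*SAP*

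**What the plan says.** SAP Table 1 ranks length of stay among recovered children as a primary non-inferiority outcome. It is counted in days from admission to the day of recovery, in recovered children only. Recovery has to be met with "absence of bilateral pitting edema for two consecutive visits, at the day of end of treatment". Under Study interventions, the SAP limits treatment for MAM: "Children will be treated for a maximum of 12 weeks and be eligible for discharge when they have achieved anthropometric recovery". The same 12-week limit is given for SAM.

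For this row, Table 4 lists "MAM: 36.4 days (SD 50.4 days)(17); 5.9 weeks (95% CI: 4.9, 7.0)(18) SAM: 56 days (assumed 41 day SD) (9". The margins are "MAM: 4.9 days; 12.5% relative margin" and "SAM: 8 days; 12.5% relative margin", in a column headed "Non-inferiority margin (relative) with $\geq 80\%$ power (Non-inferiority". The text above the table gives 360 children per arm in each severity group, 15% attrition, 76% recovery in the control arm and one-sided alpha 0.05. A footnote says the planning values come from the literature. The SAP also makes adequate power for a meaningful effect size the test for ranking an outcome as primary.

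**The concern.** A variable confined to 0 to 84 days has a limited SD. One of the two planning SDs is above that limit at any mean, and the other is close to it. An SD that the endpoint cannot have is not a usable input for its power.

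The row also has to be consistent within itself. Its SD, its number of recovered children, its margin and its power claim should follow from one another, and a day margin labelled 12.5% should be 12.5% of a stated mean. If they do not agree, a reader cannot tell what was calculated, and the stated ground for ranking length of stay as primary cannot be checked. The day margin matters most, because it may be used to judge non-inferiority: 8 days allows a longer stay on the new products than the SAP's own percentage rule does on the listed mean.

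**Working it through.** **Inputs** (SAP Table 4, its introductory text, Table 1 and Study interventions): MAM mean 36.4 days, SD 50.4, with a second MAM mean of 5.9 weeks = 41.3 days; SAM mean 56 days, SD 41; margins 4.9 and 8 days; one-sided alpha 0.05; power 80%; cap 12 weeks = 84 days.

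**1. Sample.** 360 × 0.85 = 306 per arm after attrition. 306 × 0.76 = 232.6, so about 233 recovered per arm.

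**2. Reproducing the printed margins.** With no true difference, and z(0.95) + z(0.80) = 2.4865:

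- margin at 80% power = SD × 2.4865 × √(2/n)
- power = Φ(margin / (SD × √(2/n)) − 1.645)

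| n per arm | MAM, SD 50.4: margin at 80% | MAM: power at 4.9 days | SAM, SD 41: margin at 80% | SAM: power at 8 days |
|---|---|---|---|---|
| 360 (all enrolled) | 9.3 | 36.7% | 7.6 | 83.5% |
| 306 (after attrition) | 10.1 | 32.9% | 8.2 | 77.9% |
| 233 (recovered only) | 11.6 | 27.6% | 9.5 | 67.8% |

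For n = 233, √(2/233) = 0.09265. MAM: 4.9 / (50.4 × 0.09265) − 1.645 = −0.596, and Φ = 27.6%. SAM: 8 / (41 × 0.09265) − 1.645 = 0.461, and Φ = 67.8%.

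The MAM margin is not reproduced at any of these sample sizes. The SAM margin is approached only if children who did not recover are counted.

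**3. Feasibility of the SDs.** For a variable on [a, b] with mean m, SD ≤ √((m − a)(b − m)), and never more than (b − a)/2.

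- On 0 to 84 days at any mean, the limit is 42.
- MAM at mean 36.4: √(36.4 × 47.6) = 41.6. On a three-month horizon (about 92 days) the limit at any mean is 46. The printed 50.4 exceeds all of these. At that mean it would need a cap of about 36.4 + 50.4²/36.4 = 106 days.
- SAM at mean 56: √(56 × 28) = 39.6 on 0 to 84 days, so 41 is 1.4 days above the limit. On 0 to 92 days the limit is √(56 × 36) = 44.9, and 41 is possible.

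**4. The 12.5% label.**

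- SAM: 0.125 × 56 = 7.0 days; 8/56 = 14.3%.
- MAM: 0.125 × 36.4 = 4.55 days; 4.9/36.4 = 13.5%. The average of the two listed means is (36.4 + 41.3)/2 = 38.85, and 12.5% of that is 4.86. This may be the origin of 4.9, but the SAP does not say so.

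**5. Direction of the error.** At n = 233, 4.9 days has 80% power if the SD is 4.9 / (2.4865 × 0.09265) = 21.3 or less. Eight days has it up to 34.7, and 7 days up to 30.4. If scheduled recovery cannot come before day 28 (MAM, two-weekly visits) or day 14 (SAM, weekly visits), the largest SDs at the listed means are √(8.4 × 47.6) = 20.0 and √(42 × 28) = 34.3. Power at the printed margins is then 84.1% and 80.9%. Those minimum stays are inferred from the two-visit rule and the visit schedule; neither document states them.

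**The case against.** The best defence is that these are literature inputs, perhaps correctly transcribed from studies with another treatment limit or population, and that the SAP openly labels the SAM value as assumed. The planning SD does not enter the regression analysis, and an SD that is too large understates power, so the error is conservative. All of this stands. It explains how the numbers could have arisen, but it does not make them SDs of this endpoint.

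A reader might infer three stronger things that the documents do not support.

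- **That the SAM SD is strictly impossible.** It is below the mean-free limit of 42. It breaks the limit at mean 56 only if stay stops at day 84. The SAP's non-response definition refers to three months of follow-up, and protocol Table 7 puts discharge at about week 12. Only the inferred 14-day minimum brings the three-month limit below 41, to √(42 × 36) = 38.9, and that minimum depends on visits keeping to schedule.
- **That the MAM margin was derived from SD 50.4.** No standard variant gives 4.9 days from it. A percentage of a mean fits better.
- **That the outcome is underpowered.** The 28% and 68% describe the printed inputs, not the trial. Step 5 shows that feasible SDs can restore 80% at both printed margins.

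It can also be said that 56/64 = 0.875, so 8 days is 12.5% on a reciprocal scale. The SAP does not state that scale, and it does not explain the MAM row: 36.4/0.875 gives a margin of 5.2 days and 38.85/0.875 gives 5.55, neither of which is 4.9. Finally, a margin should rest on the acceptable loss, not on what a smaller SD would permit. That is right. The case for 7 days is therefore the SAP's own 12.5% rule, not power.

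**Conclusion.** The point holds in a limited form. The MAM SD of 50.4 days cannot be the SD of stay among recovered children under the 12-week cap, nor under a three-month one. The SAM SD of 41 is borderline and should be treated as implausible, not as excluded.

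The row does not hold together. On the printed inputs, with about 233 recovered children per arm, power is about 28% (MAM) and 68% (SAM), against at least 80% in the column heading. The SAM margin is one day wider than 12.5% of its listed mean. The MAM margin matches 12.5% only of an unstated average of two means.

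This rests on the SAP's 76% recovery and 15% attrition, equal SDs across arms, no true difference, and a normal approximation. It does not show inadequate power or that the primary ranking is wrong. It shows that the row cannot serve as evidence either way until it is restated.

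**What to change.** Before unblinding, restate the length-of-stay row of SAP Table 4:

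- Replace both SDs with values feasible under the treatment limit. The blinded SD among recovered children, pooled over arms within MAM and within SAM, would serve. State the maximum stay assumed.
- State the reference mean behind each day margin, and the recovered-only n.
- Make the SAM day margin match the stated 12.5% rule: 7 days on 56. Confirm the mean that gives 4.9 days for MAM, or correct the figure.
- Recompute and print the power for each group. Use the new SD to report power, not to choose the margin.

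The cost is one table row and one blinded calculation, with no new data. The SAM margin becomes slightly stricter, and the stated power may change in either direction. Seven days has 80% power for an SD up to about 30 days, but only about 71% if the SD were as high as 34.3. If power falls short, the SAP should say so and leave the margin at the rule.

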Weight gain during treatment	MAM: 4.1 g/kg/day (SD = 3.0) (17), SAM: 3 g/kg/day (SD = 4.7) in 6-23 mo and 8.6 g/kg/day (SD = 4.7) in 24-59 mo (19)	Non-inferiority	MAM: 0.14 kg; 12.5% relative margin SAM: 0.91 g/kg/day; 12.5% relative margin		Primary
Anthropometry at discharge from treatment	MAM: All estimates from Fabiansen et al (20) WLZ: -1.52	Non-inferiority	MAM:		Primary

	
MUAC: 130.1 mm HAZ: -1.86 WAZ: -2.6 (assumed from SAM because estimates not available) Weight: 7.8 kg Height: 72.9 cm
 
SAM: All estimates from Kangas et al(9) WLZ: -1.9 MUAC: 125.9 mm HAZ: -2.3 WAZ: -2.6 Weight: 7.3 kg Height: 71.6 cm
		
WLZ: 0.2 z-scores; 12.5% relative margin MUAC: 6.8 mm; 5% relative margin HAZ: 0.2 z-scores; 12.5% relative margin WAZ: 0.4 z-scores; 12.5% relative margin Weight: 0.4 kg; 5% relative margin Height: 3.8 cm; 5% relative margin
 
SAM: WLZ: 0.3 z-scores; 12.5% relative margin MUAC: 6.3 mm; 5% relative margin HAZ: 0.3 z-scores; 12.5% relative margin WAZ: 0.4 z-scores; 12.5% relative margin Weight: 0.4 kg; 5% relative margin Height: 3.8 cm; 5% relative margin
		
Anthropometry at 3-months post-discharge	MAM: All estimates from Fabiansen et al (20)	Superiority		MAM: WLZ: 0.26	Primary

	WLZ: -1.52 MUAC: 130.1 cm HAZ: -1.86 WAZ: -2.6 (assumed from SAM because estimates not available) Weight: 7.8 kg Height: 72.9 cm  SAM: All estimates from Kangas et al(9) WLZ: -1.9 MUAC: 125.9 cm HAZ: -2.3 WAZ: -2.6 Weight: 7.3 kg Height: 71.6 cm			MUAC: 2.46 cm HAZ: 0.39 WAZ: 0.37 Weight: 0.39 kg Height: 1.87 cm  SAM: WLZ: 0.37 MUAC: 3.13 cm HAZ: 0.48 WAZ: 0.37 Weight: 0.55 kg Height: 2.76 cm	
Hemoglobin at discharge	MAM: 108 g/L (SD = 13) (21) SAM: 108.6 g/L (SD = 11.2) (22)	Non-inferiority	MAM: 2.7 g/L; 2.5% relative margin SAM: 2.2 g/L; 2.5% relative margin		Primary
Hemoglobin at 3-months post-discharge	MAM: 108.0 g/L (SD = 13) (21) SAM: 108.6 g/L (SD = 11.2) (22)	Superiority	--	MAM = 2.9 g/L SAM = 2.9 g/L	Primary
Default from treatment	MAM: 6.8% (17) SAM: 8.5% (9)	Non-inferiority	MAM: 50% relative margin SAM: 45% relative margin		Secondary
Transfer to inpatient treatment	MAM: 5.8% (20) SAM: 20.1% (9)	Non-inferiority	MAM: 70% relative margin SAM: 40% relative margin		Secondary
Non-response to treatment	MAM: 32.2% (18), 28%(20) SAM: 12.5% (9)	Non-inferiority	MAM: 30% relative margin SAM: 25% relative margin		Secondary

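### SAM weight gain: with SAP Table 4's own SD and 15% attrition, power at the 0.91 g/kg/day margin is about 77%, not 80%, and lower still if 4.7 is a within-age-band SD

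*SAP*

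**What the plan says.** SAP Table 4 gives the planning values for SAM weight gain by age band: "SAM: 3 g/kg/day (SD = 4.7) in 6-23 mo and 8.6 g/kg/day (SD = 4.7) in 24-59 mo (19"). It gives no SD for all ages together and no age mix. The margin for the whole SAM stratum is "SAM: 0.91 g/kg/day; 12.5% relative margin", in a column headed as having at least 80% power.

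The sample size is "1080 children with SAM (360 per arm) and 1080 children with MAM (360 per arm"). On top of that the SAP allows for "a loss to follow up of 15% (Table 4"). Protocol Table 4 turns this into "306 MAM and 306 SAM children in analysis after 15% attrition". Both documents use one-sided alpha 0.05 for non-inferiority.

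SAP Statistical methods splits the analysis by MAM and SAM only. The model for an endpoint such as weight gain reads: "we will use linear regression to estimate differences in that outcome between treatment arms, adjusting for any baseline factors as appropriate and health center". Under SAP Baseline characteristics, age is a candidate covariate. It enters only if the literature links it to outcome and the arms differ by at least 5% in absolute terms. The 6-23 versus 24-59 month split appears only as an exploratory sub-group analysis.

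Weight gain is secondary in Protocol Table 3 and primary in SAP Table 1. The SAP explains that it ranks as primary any outcome with adequate power for a meaningful effect.

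**The concern.** There are two separate problems. First, the 80% claim does not follow from the row's own SD once the stated attrition is applied. Second, the SD is printed per age band while the model covers all SAM children aged 6-59 months. If two groups have means of 3 and 8.6, the spread of the pooled outcome includes the gap between them, unless the model contains age. An SD valid inside a band is then too small for the planned comparison.

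Adequate power is the SAP's stated reason for ranking this outcome as primary. If power is overstated, a failure to show non-inferiority on weight gain could be read as evidence against a product when the comparison was simply too imprecise.

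**Working it through.** **Inputs.** Margin 0.91, SD 4.7, and band means 3 and 8.6 (SAP Table 4). One-sided alpha 0.05 (both documents). Enrolled 360 per arm, attrition 15%, so 360 × 0.85 = 306 analysed. The true difference is taken as zero.

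**Formula.** Power = Φ(margin / (SD × √(2/n)) − 1.645).

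**Step 1: the plan's figure with its listed SD.**
- n = 306: 4.7 × √(2/306) = 0.380; 0.91/0.380 = 2.395; Φ(0.750) = 77.3%.
- n = 360: 4.7 × √(2/360) = 0.350; 0.91/0.350 = 2.598; Φ(0.953) = 83.0%.
- 80% at this margin needs 330 analysed per arm, which is 330/0.85 = 389 enrolled.

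So the stated 80% is not reproduced at 306. It is met only with little or no attrition.

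**Step 2: the SD if 4.7 is within-band and age is not in the model.** With w the share aged 24-59 months, the all-ages SD is √(4.7² + w(1−w) × 5.6²), where 5.6 = 8.6 − 3, 4.7² = 22.09 and 5.6² = 31.36.
- w = 0.2 or 0.8: √(22.09 + 0.16 × 31.36) = √27.11 = 5.21.
- w = 0.5: √(22.09 + 0.25 × 31.36) = √29.93 = 5.47.

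**Step 3: power at margin 0.91.** The age mix is an assumption, so the range is shown.

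| Age mix (either way round) | All-ages SD | n = 306 | n = 360 |
|---|---|---|---|
| 0:100 | 4.70 | 77.3% | 83% |
| 5:95 | 4.86 | 75.0% | 81% |
| 10:90 | 4.99 | 72.9% | 79% |
| 20:80 | 5.21 | 69.7% | 76% |
| 50:50 | 5.47 | 66.0% | 72% |

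**Step 4: separating the two causes.** At 306 per arm, about 3 points of the shortfall (80 to 77.3) arise at SD 4.7 itself, from attrition. For mixes from 20:80 to 80:20, a further 8 to 11 points (77.3 to 69.7 or 66.0) come from pooling the bands.

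**The case against.** The strongest objection concerns the SD. The same value, 4.7, is printed for two bands with very different means. It may be one overall SD entered twice, and the documents cannot settle this. If it is an all-ages figure, pooling adds nothing and Step 2 falls away. Step 1 stands, because power without an age term is 77% either way.

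The plan also deals with age in part. Age and admission anthropometry are candidate covariates, and the age bands are a pre-specified sub-group. If the imbalance rule brings age in, the residual SD moves back towards 4.7. But that depends on chance imbalance, so the main model is not guaranteed an age term. It is also fair to say that the SAP's key objectives are recovery and relapse, and that its sample-size statement rests on recovery.

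A reader might infer three stronger things that the documents do not support:
- That power simply is 66-70%. This needs a within-band SD, no age term, 306 analysed and a mix between 20:80 and 80:20.
- That 0.91/0.125 = 7.28 reveals the planned age mix, about 76% older children. The row shows no derivation, and 12.5% of the 7.3 kg SAM discharge weight in the same table is 0.9125, which also rounds to 0.91.
- That the margin shrinks to 12.5% of a lower pooled mean, with far lower power. The table prints a fixed 0.91, and the rule works in both directions: 0.125 × 5.8 = 0.725 at 50:50, but 0.125 × 8.04 = 1.005 with 90% older children.

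**Conclusion.** The point holds in two parts. Without reservation about the SD, the claim of at least 80% power for SAM weight gain fails for the planned model without age: it is about 77% at 306 per arm, and 83% only with complete data. Conditionally, if 4.7 is within-band as printed and age stays out of the model, power at 306 lies between 66% and 77% according to age mix (66-70% for mixes from 20:80 to 80:20, or 72-76% if 360 are analysed).

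These figures assume equal products, the printed margin, one-sided 0.05 and no variance absorbed by the health-center term, for which the documents give no figure. The effect is on one SAP primary outcome, not on the recovery or relapse calculations. It should be corrected, but it does not undermine the trial's main questions.

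**What to change.** - Put age band (6-23 versus 24-59 months) in the SAM weight-gain model as a fixed covariate, whatever its balance between arms.
- State whether 4.7 is a within-band or an all-ages SD.
- State one absolute margin in g/kg/day and how it was obtained.
- Restate power at 306 per arm: about 77% with the age term, or 66-77% without it if 4.7 is within-band. If 4.7 proves to be an all-ages SD, 77% is the figure without the age term, and adding the term could only reduce the residual SD.

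Age is already recorded at admission and the bands are already defined for the sub-group analysis, so the cost is one model term and a few lines of SAP text, with no new data. The change should be made before the product codes are opened. The price is a stated power slightly below 80%, and the SAP should then say whether weight gain keeps its primary rank on that basis.
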